## Assessing an animal-assisted treatment program for adults with aphasia: the Persons with Aphasia Training Dogs (PATD) Program

using the positive reinforcement techniques, not on the performance of the dog. Dogs' behaviors in response to cuing are noted to provide for qualitative assessment of the participant's responsivity to the dog and so that relief (e.g., break for walk or play) may be immediately provided to the dog if signs of stress, fatigue, etc. are observed.

**Statistical Considerations:** Scores from weekly probes will allow for analysis of change in level of 'competence' over time, as determined using the *PPAHE* for that skill. For the purpose of statistical analyses of weekly evaluations, three scores (0= "not ready", 1= "ok", 2= best") will be dichotomized as competent (1 or 2) vs. not competent (0). In addition to the weekly evaluations, at the end of the training period, each participant will receive a summative score on the adapted *PPAHE*. This score may range from 0 to 10. In keeping with our a priori hypothesis that participants will be able to independently cue a dog to perform a minimum of 4 out of 5 obedience behaviors, a score of 5/10 points corresponds with achieving a minimum of a 1 ("ok") on all five targeted obedience behaviors or achieving a 2 ("best") on at least one behavior and 1 on three others. For the primary analysis, the proportion of subjects that successfully completed the training will be quantified with the corresponding two-sided 90% exact binomial confidence interval. For the secondary analysis, (i) the median cumulative score will be computed with the corresponding two-sided 90% distribution-free confidence interval (Hahn & Meeker, 2011) and (ii) the weekly competence scores will be analyzed using the repeated measures logistic regression model. With the total sample size of 20 subjects, the width of the two-sided 90% exact binomial confidence interval is at most 0.38 if the observed proportion of subjects successfully completed the training is 0.5. The interval is narrower if the observed proportion of successes is higher (or lower) than 0.5.

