### Preliminary Data:

The training procedures and lesson plans have been validated through use with four individuals with post-stroke aphasia (one with right-sided hemiplegia) who completed training and immediate post-treatment evaluation. Three participants worked with a family dog and the fourth participated in the program at the PSPCA. Consistent with our hypothesis, on program completion all four participants demonstrated ability to cue their dog(s) to perform a minimum of four out of five obedience skills commensurate with a handler skill level at or above a '1' on the *PPAHE*.

**Specific Aim 2: Define participant characteristics associated with recruitment, retention, compliance and program acceptability/satisfaction relevant for determining PATD candidacy.** *Hypothesis 2:* PWA will demonstrate high (above 80%) retention and compliance rates, and high program satisfaction, including increases in self-reported ratings of psychosocial well-being. To test this hypothesis, our primary outcome measure will be the *Assessment of Living with Aphasia* (Kagan et al., 2010), complemented by self-report of participants' PATD experience gathered through an ALA-modeled qualitative spoken interview and a written, aphasia-friendly, satisfaction survey.

**Rationale:** Our second hypothesis is supported by a growing literature regarding the physiological and psychosocial benefits of human-dog interaction (Friedmann & Son, 2009; Lundqvist et al., 2017; Odendaal & Meintjes, 2003) and the likely mechanisms of action for AAT, which include as Beetz (2017) described, "promoting the preconditions of learning" (p. 7) by increasing intrinsic motivation, attention, and positive mood and decreasing fear and stress (Beetz, 2017; Blakemore & Frith, 2005; Wholfarth et al., 2013). The direct and

Assessing an animal-assisted treatment program for adults with aphasia:  
the Persons with Aphasia Training Dogs (PATD) Program

regular interaction with dogs provided in the PATD program also provides for 'active engagement' with the animal, which may support greater potential for deriving these benefits than simply having the dog present (Dietz et al., 2012).

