**Outcome Measurement/Participation Timeline:** Participants will be randomized into immediate and waitlist treatment groups using permuted block randomization with stratification. Analysis between these two arms will be exploratory only in nature, and will inform us regarding the feasibility of the waitlist control design for use in a larger clinical trial. All participants will be evaluated before training begins, immediately following training, and at a 3-month follow-up. Participants in the delayed arm will participate in two pre-training evaluations, one immediately upon enrollment and one at the end of the delay period immediately before beginning training.

Week	1	2	3	4	5	6	7	8	9	10	11	12	13	
Immediate	Pre-training eval.	Skill 1	Skill 2	Skill 3	Skill 4	Skill 5	Post-training eval.							Follow-up eval. (week 19)
Waitlist	Pre-training eval.						Pre-training eval.	Skill 1	Skill 2	Skill 3	Skill 4	Skill 5	Post Training Eval.	Follow-up eval. (week 25)

**Statistical Considerations:** Primary outcome evaluation will be done with the entire sample of twenty. The mean pre-to-post-training change in each *ALA* domain score will be computed with the corresponding 90% confidence interval. With the total sample size of 20 subjects, the width of the two-sided 90% confidence interval is equal to 0.39 standard deviations of the pre-to-post-training changes. For the secondary analysis, we will evaluate the mean difference in each *ALA* domain scores between the immediate and delayed treatment arms at week 7 using the two-sided 90% confidence interval and two-sided two-sample t-test with alpha 0.1 (reflective of the small size pilot study). The results of comparison between the immediate and delayed treatment arms will be used to inform a future larger clinical trial. Qualitative data derived from narratives produced by PWA during administration of the PATD *ALA*-supplement will be orthographically-transcribed for offline analysis consistent with procedures detailed by Luck & Rose, 2007.

**Scientific rigor:** Participants will be assessed by a certified speech-language pathologist (SLP) who is not involved in PATD training. All assessment sessions will be video-recorded. A portion (approximately 20%) of the data will be selected for evaluation of intra- and inter-rater reliability. Inter-rater reliability will be conducted

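### The 0.39 SD given as the width of the 90% confidence interval for the mean ALA change is the half-width; the full width with 20 participants is 0.77 SD

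*Combined protocol and SAP*

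**What the plan says.** Specific Aim 2 names the ALA as its primary outcome measure. Under that aim's Statistical Considerations the plan says "Primary outcome evaluation will be done with the entire sample of twenty", and that the mean pre-to-post-training change in each ALA "domain score will be computed with the corresponding 90% confidence interval". The precision statement follows. It opens "With the total sample size of 20 subjects" and continues that "the width of the two-sided 90% confidence interval is equal to 0.39 standard deviations of the pre-to-post-training changes". Statistical Design and Power repeats it with the same number, confidence level and wording. Neither place calls the figure a half-width, a margin of error or a plus-or-minus value.

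Two other statements bear on how to read it:

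- For the Aim 1 proportion, also with 20 subjects, the plan says "the width of the two-sided 90% exact binomial confidence interval is at most 0.38 if the observed proportion of subjects" completing training successfully is 0.5. This stands under Specific Aim 1 (Statistical Considerations) and again under Statistical Design and Power.
- Hypothesis 2 under Specific Aim 2 says "PWA will demonstrate high (above 80%) retention and compliance rates".

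**The concern.** The width of a two-sided interval is the distance from its lower to its upper limit. A full width of 0.39 SD at 90% confidence looks too narrow for a mean estimated from 20 people, and it is close to what the distance from the mean to one limit should be.

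The primary Aim 2 analysis is estimation, so the expected interval width is the plan's statement of what the study can deliver. It is also the only precision figure given for this outcome. Read literally, it puts the limits 0.39/2 = 0.195 SD either side of the mean. A reader would then expect an observed mean change of, say, 0.3 SD to have an interval that excludes zero. With limits at ± 0.387 SD it would include zero.

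**Working it through.** **Inputs**

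- n = 20, one group, paired change (Specific Aim 2, Statistical Considerations).
- Two-sided 90% confidence, width in SDs of the change scores (same place, and Statistical Design and Power).
- Stated width: 0.39 SD.

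**Step 1: reproduce the plan's figure.** The interval for a mean change is mean ± t(0.95, n−1) × SD/√n.

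- t(0.95, 19) = 1.7291 and √20 = 4.4721.
- Half-width = 1.7291/4.4721 = 0.3866 SD, which rounds to 0.39.
- Full width = 2 × 0.3866 = 0.7733 SD.
- Ratio of full width to stated figure = 0.7733/0.39 = 1.98.

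The plan's number is reproduced only as the half-width.

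**Step 2: try other routes to a full width of 0.39 SD at n = 20.**

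| Variant | Half-width (SD) | Full width (SD) |
|---|---|---|
| 90% two-sided, t | 0.387 | 0.773 |
| 90% two-sided, normal quantile | 0.368 | 0.736 |
| 90% two-sided, t, expected width with small-sample SD correction | 0.382 | 0.763 |
| 80% two-sided, t (same quantile as one-sided 90%) | 0.297 | 0.594 |
| 95% two-sided, t | 0.468 | 0.936 |

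None gives a full width of 0.39 SD. An interval that narrow at n = 20 has half-width 0.195 SD, so t = 0.195 × 4.4721 = 0.872 on 19 degrees of freedom, which is about 61% confidence.

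**Step 3: sample size that would make the sentence true.** Solving 2 × t(0.95, n−1)/√n ≤ 0.39 gives n = 74. If 0.39 is treated as rounded (≤ 0.395), n = 72.

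**Step 4: how the plan uses the word elsewhere.** The exact 90% binomial interval for 10 of 20 is 0.302 to 0.698. Its full width is 0.396 and its half-width 0.198. The stated 0.38 is near the full width (slightly below it) and nowhere near the half-width. So *width* means full width for the proportion and half-width for the mean change, and the two uses sit in adjacent paragraphs of Statistical Design and Power.

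**Step 5: fewer completers.** The documents do not give a number expected to complete both evaluations. As an illustration, 80% of 20 is 16; the smallest whole number above 80% is 17 (17/20 = 85%).

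| Participants with both evaluations | Half-width (SD) | Full width (SD) |
|---|---|---|
| 20 | 0.39 | 0.77 |
| 17 | 0.42 | 0.85 |
| 16 | 0.44 | 0.88 |

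**The case against.** The strongest reply is that 0.39 SD is a correct margin of error with the wrong label, and that nothing depends on it. The Protocol Synopsis bases the sample on experience with the program, the timeline and the funding, and twenty is a minimum. There is no precision target that 0.77 SD would miss. The interval finally reported will come from the data and will be right whatever this sentence says. All of this stands. It limits the consequence, but it does not make the sentence true.

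A second reply is that the plan ties the future trial to the comparison of immediate and delayed arms, whereas this figure concerns the single-group change, and later planners will have the observed SD. That narrows the harm mainly to readers judging planned precision. It does not remove it, because the Approach section presents the whole study as the foundation for a larger trial.

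The third reply concerns retention, and it is partly right. Sixteen of 20 is exactly 80%, which is the boundary and not above it. The plan does not say at which visit the 80% applies, and losses after the post-training evaluation would not reduce the pre-to-post sample. More than 20 may also be enrolled. The 16-completer figures are therefore an optional sensitivity case. The mislabelled width does not depend on them.

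**Conclusion.** The statement is wrong in both places. With 20 participants giving both evaluations, the two-sided 90% interval for the mean ALA domain change is 0.77 SD wide, not 0.39 SD, so precision is overstated about twofold. This rests on the usual one-sample t interval for paired changes; a normal quantile or a small-sample correction moves the width only to 0.74 or 0.76 SD. The likely cause is a labelling slip. The planned analysis and the sample size are unaffected. The figure still needs correcting, because it is the sole precision statement for an outcome whose primary analysis is an interval estimate. The point about incomplete data is secondary, and its size depends on an assumed number of completers.

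**What to change.** In Specific Aim 2 (Statistical Considerations) and in Statistical Design and Power, replace the sentence with wording such as: *With 20 participants completing both evaluations, the half-width of the two-sided 90% confidence interval for the mean change is 0.39 SD of the changes (full width 0.77 SD).*

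Optionally add, marked as an assumption: *If 16 complete both, the half-width is 0.44 SD (full width 0.88 SD).*

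The cost is two edited sentences and a less favourable stated precision. No change to the sample size, the analysis or the conduct of the study is needed.

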**Feasibility Metrics:** We will track *recruitment rates* appropriate to the creation of a CONSORT flow diagram (e.g., Horton et al., 2016) including: # contacted, # screened, # eligible (vs. ineligible), # consented/enrolled (vs. declined).. Similarly, participant *retention rates* will be tracked including: # completing baseline assessment, # completing immediate post-treatment assessment, and # completing follow-up assessment. Participant withdrawals will be tracked for whether initiated by researcher or participant. Participant *compliance rates* will be tracked including # assessment and training sessions (relative to total possible) completed, and # self-reported home practice sessions.

**Outcome Measurement:** The primary quantitative outcome measure of acceptability, the *ALA*, is a pictographic self-report measure of quality of life developed to assess the impact of aphasia on daily life. Questions address participants' perceptions of aphasia, their environment, their relationships, their community engagement, experiences of self-confidence and respect, and their progress toward "living well with aphasia". Participants respond by pointing to a visual analog scale, providing for quantification of responses, and rendering the tool accessible to those with language impairment. Overall score and subdomain scores have demonstrated acceptable-to-high test-retest reliability and internal consistency (Simmons-Mackie et al., 2014). To augment standardized evaluation, the PI has developed a complementary interview, consistent with the format of the *ALA*, to more specifically probe PATD participants' perceptions of the impact of the training program. Participant narratives produced during the administration will be supported using interviewing strategies appropriate for persons with aphasia (Luck & Rose, 2007). A written, visual analog scale satisfaction survey designed to adhere to guidelines of 'aphasia-friendly' written materials will also be administered. We anticipate the assessment battery will take approximately 3 hours to complete.

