## Assessing an animal-assisted treatment program for adults with aphasia: the Persons with Aphasia Training Dogs (PATD) Program

Participants will be informed that they may withdraw from the study at any time, without penalty, and contact personnel are provided on the consent form. Participants will be informed that they can contact the PI at a later time if they would like to spend time reviewing the information in order to avoid them feeling pressured to participate. They will also be informed that pre- or post-consent screening or behavioral test results may indicate that they are not eligible to continue with the study. Pre-consent, research candidates from outside of the MRRI Research Registry will be screened to confirm diagnosis and related medical information and for geographic eligibility.

Assignment into each arm will be done using block randomization with stratification. Interested participants will be screened for one of two strata: 1) participation with a family dog or 2) participation through the Pennsylvania SPCA (PSPCA). Interested participants will be automatically assigned to the PSPCA condition if a) they do not have a family dog or b) their family dog is not eligible to participate. There will be no minimum requirement for assignment into either stratum.. As participants are enrolled in either the PATD or PATD-PSPCA condition, they will be block randomized into either immediate or waitlist treatment groups. Recruitment will be ongoing, until a minimum of ten PATD immediate and ten PATD waitlist participants have been enrolled.

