## RESEARCH DESIGN AND METHODS

### Study Procedures and Materials

Cognitive-linguistic and psychosocial assessment sessions for all groups will take place at the Moss Rehabilitation Research Institute. Participants will complete either 3 (immediate arms) or 4 (delayed arms) assessment (dx) sessions over the course of either 19 or 25 weeks, respectively (Table 1); we anticipate that each assessment session will take approximately three hours to complete. The instruments included in these assessments will be the *Assessment of Living with Aphasia* (Simmons-Mackie et al., 2014), the PATD-program ALA supplement (developed by the PI for this study, not administered in pretraining evaluation(s)) the *Confidence after Stroke Measure* (Horne et al., 2017), and the *Behavioural Assessment of Dysexecutive Syndrome* (Wilson et al., 1996). Participants will also complete at baseline the *Western Aphasia Battery-Revised* (WAB-R, Kertesz, 2006) to provide a profile of their aphasia. The WAB-R will not be repeated.

Assessing an animal-assisted treatment program for adults with aphasia:  
the Persons with Aphasia Training Dogs (PATD) Program

All participants will be evaluated before training begins, immediately following training, and at a 3-month follow-up. Participants in the delayed arm will participate in two pre-training evaluations, one immediately upon enrollment and one at the end of the delay period immediately before beginning training.

Week	1	2	3	4	5	6	7	8	9	10	11	12	13	
Immediate	Pre-training eval.	Skill 1	Skill 2	Skill 3	Skill 4	Skill 5	Post-training eval.							Follow-up eval. (week 19)
Waitlist	Pre-training eval.						Pre-training eval.	Skill 1	Skill 2	Skill 3	Skill 4	Skill 5	Post Training eval.	Follow-up eval. (week 25)

Table 1: Sequence of participation

PATD training sessions will take place either at participants' homes, for those working with a family dog, or at the PSPCA. Training sessions that take place at the PSPCA will occur in an enclosed room, in an open indoor space in which the dog is tethered or on-leash, or in a fenced-in outdoor yard.

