### Behavioral assessments

Anticipated risks are minimal and include fatigue or frustration during the behavioral sessions. To protect against fatigue, participants will be informed they may stop or take a break at any time without penalty. Participants will be invited to take breaks as necessary and reminded that they may cease participation at any time. It is recognized that some participants may demonstrate discomfort while completing the assessments of quality of life. They are informed that some of the questions they will be asked will deal with their personal experiences and emotions related to living with aphasia, and reminded that they may choose not to answer specific questions or may forego this assessment entirely. Participants may also be offered referral information

Assessing an animal-assisted treatment program for adults with aphasia:  
the Persons with Aphasia Training Dogs (PATD) Program

for psychological care, if interested. Risks associated with travel to and from behavioral assessment sessions are anticipated to be not more than those associated with urban daily life.

Dog-training

Risks associated with interaction with dogs include the possibility of physical injury and the risks associated with coming into contact with fur, saliva, waste, or zoonotic disease associated with dogs. Before beginning work with dogs, participants will be provided with guidance on universal precautions. PSPCA participants will receive a pictographic information sheet.

Dogs are screened through either owner-report (for family dogs) or PSPCA behavior staff-report for eligibility. Participants are informed that the program is directed toward training basic obedience skills, not remediation of behavior 'problems', and that the PI conducting the training is not a certified-professional dog trainer. Dogs with a reported history of bites, reactivity (e.g., barking, growling) toward strangers, or resource guarding are excluded. It is anticipated that for participants working with a family dog, risks will not be more than those otherwise experienced in regular interaction with the dog.

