To the extent that variation across the sample allows, we will explore the effects on performance of demographic (age, education) and aphasia-related (time post-onset, *WAB-R AQ*) variables. Due to the nature of the differences between PATD participation with a family dog and with shelter dogs, we will not run between-group analyses of PATD versus PATD-PSPCA participant groups.

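### The exploratory week-7 ALA comparison between arms ignores the week-1 ALA score that both arms already provide, so it probably gives up precision

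*Combined protocol and SAP*

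**What the plan says.** The Statistical Considerations under Specific Aim 2 define a secondary analysis: the mean difference in each ALA domain score "between the immediate and delayed treatment arms at week 7 using the two-sided 90% confidence interval and two-sided two-sample t-test", at alpha 0.1. Statistical Design and Power repeats it. Neither place names a baseline covariate, a change score or the randomisation stratum. The same paragraphs do specify pre-to-post change for the primary ALA analysis, so the natural reading is that the arm comparison uses week-7 scores as they stand.

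Other relevant statements:

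- **Status.** The participation timeline says "Analysis between these two arms will be exploratory only in nature". The plan also says that the results will inform a larger trial.
- **Baseline data.** The schedule gives both arms a pre-training evaluation in week 1. Study Procedures and Materials states "Participants in the delayed arm will participate in two pre-training evaluations, one immediately upon enrollment and one at the end of the delay period", and lists the ALA among the instruments used at these sessions.
- **Reliability.** Outcome Measurement says of the ALA: "Overall score and subdomain scores have demonstrated acceptable-to-high test-retest reliability and internal consistency". No coefficient is given.
- **Sample size.** Recruitment continues "until a minimum of ten PATD immediate and ten PATD waitlist participants have been enrolled".
- **Other covariates.** The end of Statistical Design and Power lists age, education, time post-onset and WAB-R AQ for exploration. The week-1 ALA score is not among them.

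**The concern.** At week 7 the immediate arm has just finished training and the waitlist arm has not started. This is the only randomised contrast of trained with untrained participants in the study. With about 10 per arm, much of the spread in week-7 scores will be stable differences between people that were already present in week 1. The t-test treats all of that spread as noise. Regressing on the week-1 score removes the part that week 1 predicts.

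The matter is efficiency, not validity. Randomisation makes the unadjusted difference unbiased, and its interval already allows for chance baseline differences. At stake is the usefulness of the estimate handed to the next trial. An analysis without baseline also leaves out two quantities useful for planning that trial: the residual SD after adjustment and the week-1 to week-7 correlation.

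**Working it through.** **The plan's own figures.** The plan states no width, power or effect size for this comparison. The nearest figure is 0.39 SD for the within-subject ALA change with n = 20. It reproduces as t(0.95, 19)/√20 = 1.729/4.472 = 0.387, which is a half-width (the full width is 0.773). The widths below are full widths unless marked otherwise.

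**Inputs.**

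- 10 per arm (Recruitment)
- two-sided 90% interval and alpha 0.10 (Statistical Considerations)
- week-1 to week-7 correlation r within arm: not in the documents, assumed from 0 to 0.8
- scores scaled so that the week-7 SD is 1

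**Formulas for the half-width.**

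- t-test: t(0.95, 18) × √(2/10) = 1.734 × 0.447 = 0.775, so the full width is 1.55.
- ANCOVA: t(0.95, 17) × √[(2/10)(1 − r²)(17/16)]. The factor 17/16 is the expected variance inflation from chance imbalance in one normal covariate with 20 participants.
- Example at r = 0.7: 1.740 × √(0.2 × 0.51 × 1.0625) = 1.740 × 0.329 = 0.573.

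At r = 0, 0.3, 0.5 and 0.8 the ANCOVA half-widths are 0.802, 0.765, 0.694 and 0.481. Setting the two formulas equal gives 1 − r² = (1.7341/1.7396)² × 16/17 = 0.935, so break-even is at r ≈ 0.25.

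**Simulation.** 40,000 trials per setting, bivariate normal scores with SD 1, 10 per arm. The mean t-test width is 1.53, not 1.55, because the simulation averages over sample SDs while the formula uses the true SD.

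| r | t-test | ANCOVA | Change | ANCOVA + stratum |
|---|---|---|---|---|
| 0 | 1.53 | 1.58 | 3% wider | 1.59 |
| 0.25 | 1.53 | 1.53 | none | 1.54 |
| 0.3 | 1.53 | 1.51 | 2% narrower | 1.51 |
| 0.5 | 1.53 | 1.37 | 11% narrower | 1.38 |
| 0.7 | 1.53 | 1.13 | 26% narrower | 1.13 |
| 0.8 | 1.53 | 0.95 | 38% narrower | 0.95 |

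Type I error is about 10% for all three analyses. When the stratum is not prognostic, adding it changes the ANCOVA width by less than 1%.

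**Detectable difference.** By the noncentral t distribution at 80% power, it is 1.16 SD for the t-test, and 1.03, 0.85 and 0.72 SD for ANCOVA at r = 0.5, 0.7 and 0.8.

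**Missing week-1 scores.** The ANCOVA drops anyone without a week-1 domain score; the t-test keeps them. Compare with 1.53 for the t-test on all 20:

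| Week-1 score missing | r = 0.3 | r = 0.5 | r = 0.7 | r = 0.8 |
|---|---|---|---|---|
| 1 per arm (ANCOVA on 9 v 9) | 1.60 | 1.46 | 1.20 | 1.01 |
| 2 per arm (ANCOVA on 8 v 8) | 1.72 | 1.57 | 1.29 | 1.08 |

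With two missing per arm the gain is gone at r = 0.5 and remains at r = 0.7 and above.

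**If dog source were prognostic.** As an illustration only, assume a stratum effect of 0.8 within-stratum SD at both visits, with half the sample in each stratum, balanced across arms. The t-test is then conservative, with type I error about 7.5% against a nominal 10%. ANCOVA on week 1 alone gives 9.1% to 9.7%, and adding the stratum gives 9.9% to 10.1% (r = 0.3 to 0.7).

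**The case against.** The strongest reply is that nothing here is an error. The t-test is valid, the comparison is declared exploratory, no hypothesis rests on it, and the primary ALA analysis already uses baseline through within-subject change. The stated purpose of the two arms is partly to test whether a waitlist design is feasible, which a narrower interval does little to answer. Even at r = 0.7 the interval is 1.13 SD wide, too wide to settle an effect size. All of this stands and limits the weight of the point. It does not remove it, because the plan also says that the results will inform a larger trial.

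A second reply is that the gain rests on an unknown correlation. Test-retest reliability is not the same as a six-week correlation when one arm is trained in between, since varied response would lower it. The widths above are also averages: in a single trial the ANCOVA interval is wider than the t interval in 51% of cases at r = 0.3, 20% at r = 0.5 and 3% at r = 0.7. This is fair, and it is why the gain is given as a range. Against it, participants are at least six months post-onset and must be medically and neurologically stable, and the ALA's reliability is described as acceptable to high. A correlation above 0.25 is a reasonable expectation, though not a documented fact. The simulations also assume normal scores, a common slope and equal variances.

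A third reply is that complete-case ANCOVA loses participants. On the quality-of-life assessments, they are told that "they may choose not to answer specific questions or may forego this assessment entirely". This also stands: two missing week-1 scores per arm would make the adjusted estimate the less precise one at r = 0.5. It is the reason to show the unadjusted estimate alongside.

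**Conclusion.** The point holds as one of likely lost precision, not of bias. The week-7 comparison leaves out a baseline measurement of the same outcome that is collected in both arms. With 10 complete participants per arm, adjustment would narrow the 90% interval by about 11% to 38% if r lies between 0.5 and 0.8. It would make almost no difference near 0.25 to 0.3, and would widen the interval by 3% at r = 0. The omission is certain from the text; the size of the gain depends on r, which the documents do not give, and on few week-1 scores being missing. The change should be made before analysis because it costs almost nothing, but the study's main conclusions do not depend on it.

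**What to change.** In the Specific Aim 2 Statistical Considerations and in Statistical Design and Power, replace the two-sample t-test with an ANCOVA for each ALA domain:

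- Regress the week-7 score on arm and the week-1 score of the same domain. For the waitlist arm, week 1 is the evaluation at enrolment; its second pre-training evaluation is the week-7 outcome.
- Add the randomisation stratum only if both strata contain participants in both arms, and state that rule in advance. It is needed because "There will be no minimum requirement for assignment into either stratum". Using stratum as a covariate is compatible with the statement that "we will not run between-group analyses of PATD versus PATD-PSPCA participant groups", since the two dog-source groups are not being compared.
- Report the adjusted difference with its 90% interval at alpha 0.1, name it in advance as the main estimate, and keep the comparison labelled exploratory.
- Show the unadjusted difference beside it, with the number analysed in each.
- Report the residual SD and the week-1 to week-7 correlation for planning the larger trial.

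The cost is a change of wording and one regression per domain. Residual degrees of freedom fall from 18 to 17, or to 16 with the stratum term. No new data are needed.
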